14.3 Analysis of Primary Endpoint

The primary outcome is the % change in FEV1 from the start to the end of the treatment period (either placebo or 20% NAC). The first analysis will be to test the assumption of negligible carryover effects from study period 1 to period 2. We will compare the sum of the outcome values measured in the two periods for each participant across the 2 sequence groups (placebo-20% vs. 20%-placebo) using an unpaired t-test. After no or negligible carryover effect has been confirmed, we will test for the difference in treatment effects between placebo and 20% NAC using a paired t-test.

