14.4 Analysis of Secondary Endpoints

As a secondary outcome, we will include an analysis that examines the change associated with the 7-day treatment with 0.9% saline. Our secondary analysis is to determine the characteristics of participants that respond to NAC. We will classify participants in four groups based on their post-bronchodilator FEV1 in response to NAC. FEV1 of 0-4% change will define non-responders and FEV1 of 5-9%, 10-14%, or > 15% will define the 3 categories of responders. We will examine NAC responders and non-responders to determine if baseline CT mucus scores, lung function measures, or sputum G' measures predict treatment response. We will construct ROC curves to determine the CT score that predicts NAC response thereby identifying a CT biomarker for future thiol saccharide trials. In addition, we will examine how the CT mucus score changes with NAC treatment using a subset of the participants following second period treatment. Finding a decrease in CT score in the 20% NAC group compared to the placebo group will provide support for

 our hypothesis that NAC improves lung function by decreasing intraluminal mucus. Other analyses will be to examine the effects of treatment on sputum elasticity (G').

Safety and tolerability data will be summarized by treatment group.

Adverse event rates will be coded by body system and MedDra classification term. Adverse events will be tabulated by treatment group and will include the number of patients for whom the event occurred, the rate of occurrence, and the severity and relationship to study drug.

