14.6 Sample Size and Randomization

We propose a sample size of 30, which will provide us with the power to examine the effect of NAC in a subgroup of individuals with asthma who have CT evidence of intraluminal mucus and to identify the CT mucus score that performs best as a biomarker of treatment response to NAC. Participants will be enrolled if their CT mucus scores are >3.0. To calculate sample size for the one-week treatment period study, we used FEV1 measures from 219 adults with asthma published in Corren et al. NEJM, 2011¹. The authors found that the standard deviation for the change in FEV1 in liters from day 1 to day 7 was 19%. Using a standard deviation of 19 and a two-sided alpha of 0.05, we calculate a sample size of 30 to have 80% power to detect a change in FEV1 of 10% (a reasonable effect size because early studies of Pulmozyme in CF reported a 10% increase in FEV1 at day 3 of treatment).

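### Section 14.4 asks whether CT score predicts NAC response but sets no criterion for the answer, then treats drawing the ROC curve as having identified a biomarker

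*Combined protocol and SAP*

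**What the plan says.** Section 14.4 (Analysis of Secondary Endpoints) groups participants by their change in post-bronchodilator FEV1 on NAC. It then says that responders and non-responders will be examined to see if baseline CT score, lung function or sputum G' predicts response. The next sentence reads: "We will construct ROC curves to determine the CT score that predicts NAC response thereby identifying a CT biomarker for future thiol saccharide trials".

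Section 14.6 (Sample Size and Randomization) gives this aim as part of the case for 30 participants: "to identify the CT mucus score that performs best as a biomarker of treatment response to NAC". Its only calculation concerns the FEV1 comparison: "Using a standard deviation of 19 and a two-sided alpha of 0.05, we calculate a sample size of 30 to have 80% power".

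For the ROC analysis the document gives no minimum AUC, confidence interval, test, alpha, cut-off index or internal validation. It does not describe a result in which no cut-off is put forward. The opening of Section 14 says that a detailed SAP will be written before the final analysis.

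**The concern.** Every data set has a best-performing point on its ROC curve. If finding that point is what identifies the biomarker, a CT score that carries no information can still produce one. The accuracy attached to it will also be too favourable, because the same participants are used to choose the cut-off and to judge it.

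The question of whether CT score predicts response does come first, but the ROC step is not made conditional on the answer, and no criterion says what answer would count as yes.

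The result is meant for use. Identifying who benefits is a secondary objective (Section 3.2), and the cut-off is intended for later thiol-saccharide trials. A cut-off passed on without a statement of its uncertainty could steer their entry criteria.

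**Working it through.** **Inputs from the document.** At most 30 participants (14.6). Entry CT score above 3 (6.2, 14.6). Scores in half-point steps, inferred from the bands in the Figure 2 legend (1.1). A change of 5% or more counts as response (14.4). SD of FEV1 change 19 (14.6).

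**Assumptions not in the document.**
- Responder share. If change is normal with SD 19, the share at or above 5% is 1 − Φ((5 − 10)/19) = 0.60 for a mean of 10, and 1 − Φ(5/19) = 0.40 for a mean of 0. The simulations covered 20–80%.
- Cut-off rule. None is stated, so several were tried.
- Score distribution. Continuous, or skewed in half-point steps above 3.

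**1. The plan's own figure.** For the paired comparison, n = (19 × (1.960 + 0.842)/10)² = 28.3, so 29. With the t distribution, n is 31, and power at 30 is 79.6%. The stated 30 is reproduced if 19 is the SD of the within-person difference. It says nothing about the ROC analysis, for which no figure is given.

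**2. Exact null result without ties.** Let J = sensitivity + specificity − 1, maximised over cut-offs, with a higher score predicting response. If CT score is unrelated to response, all orderings of responders and non-responders are equally likely. J exceeds 0 unless the ROC path never rises above the chance line.
- 15/15 split: 1 − 1/(15 + 1) = 93.8%
- 10/20 split: 1 − 1/21 = 95.2%
- Path counts for other splits: 96.1% (12/18 or 18/12), 96.0% (6/24), 96.6% (8/22)

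**3. Simulated null result** (6,000 trials per setting). With half-point tied scores, J exceeds 0 in 90–93% of trials of 30. The responder bands in 14.4 start at 0, so people whose FEV1 falls may be left unclassified. Under the assumed normal distribution that share is Φ(−10/19) = 0.30 for a mean of 10, or 0.50 for a mean of 0. About 21 or 15 people then remain, and J exceeds 0 in 89–91% of trials.

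**4. How often a cut-off is named when CT score is uninformative, by assumed rule.**

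| Assumed rule | Null trials naming a cut-off |
|---|---|
| Best point always reported | 100% |
| Best Youden point, J > 0 | 89–97% |
| AUC > 0.5 | about 50% |
| AUC ≥ 0.6 (N = 30) | 18–24% |
| AUC ≥ 0.7 (N = 30) | 3–8% |
| Two-sided 5% rank test | 4–5% |
| Lower 95% AUC bound > 0.5 | 3–4% |

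**5. Apparent accuracy when the true J is 0.** At N = 30 the median best J is 0.17–0.24. With half-point scores the mean is 0.19, and bootstrap optimism correction brings it to about 0.07. A best J of 0.4 or more occurs in about 5–8% of null trials.

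**6. Precision of the AUC.** At a true AUC of 0.5 and an 18/12 split, SE = √[(0.25 + 17 × 0.0833 + 11 × 0.0833)/(18 × 12)] = 0.109. The 95% range is 0.5 ± 1.96 × 0.109, or 0.29 to 0.71.

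**7. Price of requiring the lower AUC bound to exceed 0.5.** In simulation the requirement is met in 48–52% of trials at a true AUC of 0.70, and in 83–88% at 0.80.

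**The case against.** The strongest reply has four parts.

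- **The plan does ask the question.** The sentence before the ROC step asks whether CT score predicts response, and that can be answered no. This stands against any claim that the plan has no room for a negative result. The gap that remains is the missing criterion and the missing link from the answer to the ROC step.
- **The detail is deferred.** The SAP promised in Section 14 is the natural place for an AUC interval, a cut-off index and a bootstrap. This is fair, and it makes the repair easy. As written, though, the text tells the SAP's author that drawing the curve identifies the biomarker.
- **The analysis is secondary, in a small single-centre trial.** A hard gate would reject about half of markers with a true AUC of 0.70, which is a real loss at this stage. This stands. It argues for reporting the uncertainty and softening the claim rather than suppressing the cut-off.
- **A null cut-off would usually look weak.** A J of 0.17 is, for example, sensitivity 60% with specificity 57%, which is visibly near chance. This also stands. A reader might infer that a useless CT score would emerge with apparently useful accuracy, but a best J of 0.4 or more in about 5–8% of null trials does not support that as the usual outcome.

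**Conclusion.** The point holds as a gap in specification together with an overclaim in wording. Section 14.4 gives no criterion for deciding whether CT score predicts response, no cut-off rule and no allowance for choosing and judging the cut-off on the same people. It nonetheless describes the outcome as an identified biomarker.

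A reader might infer that the plan would name a cut-off in over 90% of trials even with an uninformative score. The document does not support that as a property of the plan, because it contains neither a Youden index nor a J > 0 rule. What can be said is that the null rate runs from about 3–5% to 100%, depending on a choice left open, and is 89–97% under that one rule. The figures also rest on the assumed responder shares and, where ties are modelled, on the assumed score distribution. Under the J > 0 rule the rate moves little across the values tried.

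The primary FEV1 comparison is unaffected. This is an inexpensive improvement that changes what the trial may conclude about CT score.

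**What to change.** In Section 14.4, and in the SAP that follows from it:

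1. Name the index used to choose the cut-off, for example Youden.
2. Report the AUC for baseline CT score with its two-sided 95% confidence interval.
3. Report bootstrap optimism-corrected sensitivity and specificity, repeating the cut-off selection in each resample.
4. Replace the clause that declares a biomarker identified with: *to propose a candidate CT cut-off requiring validation*. Bring the matching aim in Section 14.6 into line.
5. State that if the AUC interval includes 0.5, the report will say that the trial did not show that CT score predicts response, and will show any cut-off as descriptive only.

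The cost is a few sentences and a short bootstrap, with no new data or visits. Reported accuracy will be lower than the uncorrected figures. The trial may also conclude that no predictive CT score was demonstrated, which would happen about half the time at a true AUC of 0.70 and in roughly 12–17% of trials at 0.80 (100% minus the 83–88% above). Because the cut-off can still be shown descriptively, that result does not stop later trials from examining it.

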5.2 Secondary Efficacy Endpoints

We intend to examine the effect of the treatment on CT mucus score in a subset of participants. Because the CT mucus score is a novel measurement, we do not have preliminary data to describe the natural history of mucus in the airway over time or with treatment. Therefore, for the purpose of this study, we intend to describe any changes we observe.

With respect to drug tolerability, we will first analyze the two treatment periods to assess any negligible carryover effects and then describe frequencies of reported side effects.

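### Section 14.4 picks the best CT mucus score cut-off by ROC in the same 30 participants and calls the result a biomarker, with no optimism correction, no fixed responder line and no sample size basis for that aim

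*Combined protocol and SAP*

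**What the plan says.** Section 14.4 (Analysis of Secondary Endpoints) sorts participants by their change in post-bronchodilator FEV1 on NAC. Changes of 0–4% are non-response, and bands of 5–9%, 10–14% and above 15% "will define the 3 categories of responders". Responders and non-responders are then compared to "determine if baseline CT mucus scores, lung function measures, or sputum" G' predict response. CT score alone goes on to an ROC analysis: "We will construct ROC curves to determine the CT score that predicts NAC response thereby identifying a CT biomarker for future thiol saccharide trials".

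Section 14.6, with matching text in the synopsis, presents the sample of 30 as giving power "to identify the CT mucus score that performs best as a biomarker of treatment response to NAC". The calculation that follows is for the FEV1 change only: "Using a standard deviation of 19 and a two-sided alpha of 0.05", the authors arrive at "a sample size of 30 to have 80% power to detect a change in FEV1 of 10" per cent.

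For the predictor analyses the document gives no test, alpha, exploratory label, validation step or correction for choosing the cut-off. It does not say which band boundary defines response for the ROC. Section 14 promises a detailed SAP before the final analysis, which will hold any changes to this plan.

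**The concern.** A cut-off chosen because it separates responders best in 30 people will separate those same 30 people better than it would separate new patients. This happens even when the marker carries no information. Reporting the chosen cut-off with its apparent sensitivity and specificity passes that optimism on to the reader, and a p-value at the chosen cut-off has lost its nominal meaning.

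The stated purpose raises the stakes. The result is to guide later trials of a different mucolytic, so an inflated or spurious cut-off could shape their patient selection. The power statement in 14.6 adds to this, because it suggests that the sample was sized for the biomarker aim.

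**Working it through.** **1. What the stated sample size covers.** Inputs from 14.6: SD 19, difference 10, two-sided alpha 0.05, power 80%. For a paired comparison, n = (SD × (z₀.₉₇₅ + z₀.₈₀) / difference)² = (19 × (1.960 + 0.842) / 10)² = 5.32² ≈ 28.3, so 29. Exact paired-t power at n = 30 is 79.6%. The plan's 30 is therefore reproduced for the primary comparison, taking 19 as the SD of the paired difference. No term in it concerns an AUC, a cut-off or a predictor.

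**2. What 30 participants give for an AUC.** With no association, the standard error of the AUC is √[(n₁ + n₀ + 1) / (12 n₁ n₀)].
- 15 responders and 15 non-responders: √[31 / (12 × 15 × 15)] = 0.107; 1.96 × 0.107 = 0.21.
- 10 and 20: √[31 / (12 × 10 × 20)] = 0.114; 1.96 × 0.114 = 0.22.

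A null AUC of 0.5 would thus be known only to about ±0.21 to ±0.22.

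**3. Searching for the best CT cut.** Null simulation, with response independent of CT score, response SD 19 and responder line 5%. Every candidate cut is tried and judged by Fisher's test at two-sided 0.05 and by the Youden index (sensitivity + specificity − 1, true value 0).

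| CT scores assumed | Mean response | Trials | Best cut p < 0.05 | Mean best Youden index |
|---|---|---|---|---|
| Right-skewed, 3.5 to 20 | 0 or 10 | 1,500 per setting | 14–16% | 0.18–0.19 |
| No ties, at least 3 people each side of the cut | 5 | 3,000 | 20.8% | 0.20 |

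A further null run gave about 0.18 and 14–18%. The range is therefore about 14–21%, with apparent performance of about 0.18–0.20 where there is none.

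**4. Several predictors at one responder line.** Take one measure from each of the three predictor types, each tested by Mann-Whitney at two-sided 0.05.
- Independent tests at exactly 5%: 1 − 0.95³ = 14.3%.
- One such test at n = 30 rejects in 4.3–5.0% of simulated trials. At 4.6%, 1 − 0.954³ = 13.2%.
- Simulated, 1,500 trials per setting, predictor correlation 0 to 0.8: 9–13%.
- Simulated, 20,000 trials per setting, correlation 0 to 0.7: 10–13%.

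**5. If the 10% and 15% lines were also tested.** CT score alone would give about 8–11%, and three predictors about 18–28%. These rates apply only if those extra tests are run.

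**6. A gap at the responder line.** The bands in 14.4 start at 0%, so a fall in FEV1 has no category. With normal changes and SD 19, half of participants would fall below zero if the mean change is 0. If the mean is 10, the share is P(Z < −10/19) = P(Z < −0.53) ≈ 30%. The simulations count these people as non-responders, which the plan does not say.

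**The case against.** The strongest reply is that this is a secondary analysis in a 30-person, single-center study. Its marker feeds later trials, where it could be tested again, and a detailed SAP is promised. The primary test keeps its error rate. All of that stands, and it limits the weight of the point. It does not remove it: 14.4 still says that a biomarker is identified, and nothing in section 14 commits the later SAP to correcting for the search.

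A reader might infer more than the documents support:
- **Nine tests, with a false-predictor risk of 20% or more.** The plan compares responders with non-responders, which reads most naturally as one split at 5%. The higher bands subdivide the responders, and nothing says that each predictor is rerun at each boundary.
- **No lead predictor at all.** CT score is the only predictor given an ROC and the only one in the sample size text. The synopsis places sputum rheology under other evaluations. The order exists in substance, though not as a label.
- **A contradiction over CT score change.** Section 5.2 says that "for the purpose of this study, we intend to describe any changes we observe", while 14.4 would take a decrease on NAC relative to placebo as support for the mechanism. Neither names a test, and a described difference can lend support, so the conflict is weak.
- **A need for formal multiplicity control.** Holm or an ordered alpha among secondary predictors is a trade-off here. Its absence is not an error.

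It is also fair to object that the error rates are not document figures. Section 14.4 states no alpha or test, and the SD of 19 is quoted for change in FEV1, while response is defined on post-bronchodilator FEV1. They are shown as conditional ranges for that reason.

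**Conclusion.** The concern holds for the cut-off search and for the strength of the claim. Followed as written, the plan would report a CT cut-off with flattering performance, call it a biomarker and cite a power basis that was never calculated. With no true association, the apparent Youden index averages about 0.18, a nominally significant best cut turns up in about 14–21% of trials, and three predictors at one line produce a false finding in about 9–13%.

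These figures assume N = 30, SD 19, a single 5% line with falls counted as non-response, two-sided 0.05 per test and one measure per predictor type. The 0.18 also assumes skewed CT scores. More than one lung function or G' measure would raise the last figure.

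**What to change.** In 14.4:
- Make baseline CT mucus score against NAC response, split at the plan's 5% line, the single lead predictor analysis. State that participants whose FEV1 falls count as non-responders, and close the gaps between bands.
- Report the AUC with a confidence interval.
- Report the chosen cut-off's sensitivity and specificity after a bootstrap optimism correction. Each resample must repeat the cut-off search, and its cut-off is then applied to the full data. The average loss of performance is subtracted from the apparent values.
- Label the other predictors and the higher response bands exploratory.
- Replace the closing claim of the ROC sentence with wording such as: *to propose a candidate CT mucus score cut-off for confirmation in future trials*.

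In 14.6 and the synopsis, remove the statement that 30 participants give power for the biomarker aim, or restate it as the precision expected for the AUC.

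The cost is wording and one bootstrap routine, with no new participants or data. The downside is that the biomarker claim drops to candidate status and the reported performance will look less favourable.

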14.5 Interim Analysis

When approximately 50% of patients have completed the study through Visit 6, an interim analysis for safety will be conducted by the UCSF Airway Clinical Research Study Quality Assurance Committee. Serious adverse events will be monitored by the committee on an ongoing basis throughout the study.

14.6 Sample Size and Randomization

We propose a sample size of 30, which will provide us with the power to examine the effect of NAC in a subgroup of individuals with asthma who have CT evidence of intraluminal mucus and to identify the CT mucus score that performs best as a biomarker of treatment response to NAC. Participants will be enrolled if their CT mucus scores are >3.0. To calculate sample size for the one-week treatment period study, we used FEV1 measures from 219 adults with asthma published in Corren et al. NEJM, 2011¹. The authors found that the standard deviation for the change in FEV1 in liters from day 1 to day 7 was 19%. Using a standard deviation of 19 and a two-sided alpha of 0.05, we calculate a sample size of 30 to have 80% power to detect a change in FEV1 of 10% (a reasonable effect size because early studies of Pulmozyme in CF reported a 10% increase in FEV1 at day 3 of treatment).

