6.2 Inclusion Criteria

- 1. Male or female between the ages of 18 and 70 years of age at Visit 0.
- 2. Able to perform reproducible spirometry according to ATS criteria
- 3. Clinical history consistent with moderate to severe asthma for 1 year or greater.
- 4. Post-bronchodilator FEV1 <90% of predicted
- 5. Prescription and daily use of inhaled corticosteroid (ICS) equivalent to 80mcg of beclomethasone or greater
- 6. CT mucus score >3 (determined during the initial screening process, provided the prior two conditions are met)
- 7. Written informed consent obtained from participant and ability for participant to comply with the requirements of the study.

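### The plan says 30 participants give the power to identify the best CT mucus score, but no calculation supports this and the planned ROC analysis could not locate a cut-off

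*Combined protocol and SAP*

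**What the plan says.** Section 14.6 (Sample Size and Randomization) opens: "We propose a sample size of 30, which will provide us with the power to examine the effect of NAC in a subgroup", namely people with asthma and CT evidence of mucus. It attaches a second purpose to the same sample size and the same word, power: "to identify the CT mucus score that performs best as a biomarker of treatment response to NAC". The synopsis row on the rationale for the number of participants repeats this.

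The calculation that follows concerns FEV1 only. Its inputs are an SD of 19 and a two-sided 5% significance level, and its result is stated as "we calculate a sample size of 30 to have 80% power to detect a change in FEV1 of 10" per cent. It supports the primary comparison in section 14.3, where "we will test for the difference in treatment effects between placebo and 20% NAC using a paired t-test".

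The biomarker analysis is in section 14.4. Participants are grouped by post-bronchodilator FEV1 change on NAC: 0–4% is non-response, and three bands from 5% upward are response. Then "We will construct ROC curves to determine the CT score that predicts NAC response", with the stated purpose of providing a CT biomarker for later thiol saccharide trials. No expected AUC, responder rate, interval, cut-off precision or validation step is given.

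Entry is restricted on the biomarker itself. Section 6.2 lists "CT mucus score >3 (determined during the initial screening process" among the inclusion criteria, and section 14.6 repeats "Participants will be enrolled if their CT mucus scores are >3.0".

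**The concern.** A sample size justified for one comparison is credited with the power to do something different and harder. Testing a mean difference asks whether an average departs from zero. Identifying the best score asks where along a scale responders separate from non-responders, and an ROC curve in 30 people estimates that poorly.

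The consequence is practical. The chosen score is intended to select patients for later trials. A cut-off picked as the best-looking point on a small ROC curve shows some apparent discrimination even when CT score predicts nothing, and it moves widely from sample to sample when CT score does predict response.

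There is a second weakness in the same analysis. Response is defined on the NAC period alone, although every participant also supplies a saline period. A person whose FEV1 would have risen anyway counts as a NAC responder, so the curve may describe who varies rather than who benefits from NAC.

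**Working it through.** **1. The plan's own figure.** Inputs from section 14.6: SD 19, difference 10, two-sided alpha 0.05, power 80%.

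n = (SD × (z0.975 + z0.80) / difference)² = (19 × (1.960 + 0.842) / 10)² = 28.3, so 29. The noncentral-t power at n = 30 is 79.6%. The stated 30 reproduces if 19 is taken as the SD of the within-person difference. None of these inputs concerns CT score or an ROC curve.

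**2. Responder split (assumption).** The documents give no responder rate. With SD 19, a normal distribution and a 5% threshold, the share of responders is 1 − Φ(5/19) = 40% if the mean change is 0, and 1 − Φ(−5/19) = 60% if it is 10. Splits from 15:15 to 10:20 (responders:non-responders) are used below. A 20:10 split gives half-widths no wider than the 10:20 column. Treating response as binary at 5% is the natural reading of section 14.4, which contrasts responders with non-responders; it is not stated outright.

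**3. Precision of the AUC (Hanley–McNeil).** For true AUC A, with n1 responders and n0 non-responders:

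SE² = [A(1−A) + (n1−1)(a−A²) + (n0−1)(b−A²)] / (n1·n0), with a = A/(2−A) and b = 2A²/(1+A).

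At A = 0.70 and 15:15: a = 0.5385, b = 0.5765, A² = 0.49. SE² = [0.21 + 14(0.0485) + 14(0.0865)] / 225 = 0.00933, so SE = 0.097 and the half-width is 1.96 × SE = 0.19.

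| True AUC (assumed) | Half-width, 15:15 | Half-width, 10:20 |
|---|---|---|
| 0.60 | 0.21 | 0.22 |
| 0.70 | 0.19 | 0.21 |
| 0.75 | 0.18 | 0.20 |
| 0.80 | 0.16 | 0.18 |
| 0.90 | 0.12 | 0.14 |

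For a half-width of 0.10 with an even split, the total needed is about 106 at AUC 0.70 and 78 at AUC 0.80.

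**4. Power to show that the AUC exceeds 0.5.** Power = Φ((A − 0.5 − 1.96·SE0) / SE), where SE0 = 0.107 is the standard error at A = 0.5 and 15:15.

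- A = 0.70: (0.20 − 0.210) / 0.097 = −0.10, power 46%.
- A = 0.80: (0.30 − 0.210) / 0.082 = 1.09, power 86%.

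**5. Location of the cut-off (simulation, normal scores in each group, n = 30).** At a true AUC of 0.75 and 15:15, the Youden-optimal cut-off has a 95% range from about the 19th to the 82nd percentile of enrolled scores; repeat runs agree to within about two points. When CT score is unrelated to response, the best cut-off still shows a mean apparent Youden index of about 0.2, where the true value is 0.

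**6. The continuous alternative.** Power for a correlation r with n = 30 is Φ(atanh(r)·√27 − 1.96).

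- If the outcome is NAC-period change: r = 0.4 gives Φ(0.24) = 60%, and r = 0.5 gives Φ(0.89) = 81%.
- If the outcome is NAC minus saline, and the saline change has equal variance and is independent of both NAC change and CT score (assumption), r shrinks by √2. Then 0.4 becomes 0.28 and power is 33%; 0.5 becomes 0.35 and power is 48%. Positive correlation between the periods would reduce this loss.

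**The case against.** The strongest reply is that this is a secondary aim, that section 14 promises a detailed SAP before the final analysis, and that the primary result is untouched. All of that stands. It lowers the priority of the point but does not supply the missing support for a claim made twice.

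A reader might go further than the documents allow in three ways.

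- **That the AUC will be known only to ±0.2, so the trial can say nothing about the marker.** That width depends on an assumed AUC and split, neither of which is in the documents. A strong marker would be estimated more tightly and would probably be shown to beat chance.
- **That enrolling only scores above 3 is a flaw.** It is deliberate, disclosed enrichment, stated beside the biomarker sentence, and the plan claims no answer for lower scores. Section 1.1 describes scores as high as 15–19, so there is a range in which to look. The restriction limits interpretation only.
- **That a continuous analysis turns 46% power into 60% or 81%.** Those figures are for different effect sizes: under a bivariate normal with a median split, r = 0.4 and 0.5 correspond to AUCs of about 0.68 and 0.73. They also apply to NAC-period change, not to the NAC-minus-saline difference recommended here.

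It is also fair to say that a regression slope gives no threshold, so the ROC still has a place if a cut-off is wanted for later trials.

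**Conclusion.** The concern holds as a matter of an unsupported claim. The sample size reproduces for mean FEV1 change and for nothing else. Under the splits assumed above, 30 people could show that a strong marker (AUC about 0.80 or more) discriminates better than chance, but could not say which score performs best. Even at an AUC of 0.75 the selected cut-off spans most of the enrolled range.

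The AUCs, the splits and the normal score distributions are assumptions. The absence of any biomarker calculation, and the definition of response on the NAC period alone, are read directly from the plan. This should be corrected, but it does not threaten the primary analysis.

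**What to change.** 1. In section 14.6 and in the synopsis, delete the biomarker power claim, or replace it with the AUC precision range above and label the aim exploratory. Change both places, so that they stay consistent.
2. In section 14.4, make the main predictor analysis a regression of each participant's NAC-minus-saline FEV1 change on baseline CT score, kept continuous. This uses the crossover's own control. Once the two periods are differenced, the slope on CT score is the treatment-by-score effect, so no separate interaction term is needed.
3. Keep the ROC curve as exploratory, with bootstrap intervals for the AUC and the cut-off and an optimism correction.
4. State that conclusions apply to CT scores above 3.

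The cost is protocol and SAP wording, with no added participants, visits or scans. The downsides are a more modest claim and the noise added by subtracting the saline period. If a power figure is given for the regression, it should be for the differenced outcome (about 33% or 48% under the independence assumption in the working), not 60% or 81%.
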